## ***8.2 Covariates and strata***

No stratified analyses are planned for this study.

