## ***8.3 Subgroups***

For the efficacy analysis, the subgroup of images with overlying tissue will be explored. In this subgroup, the depth will be measured via the amount of overlying tissue that there can be to still maintain the ratio of nerve to non-nerves. Other subgroup analyses will be presented by cohorts and by cameras (OnLume or Zeiss). Both cameras are able to capture WLR and FL lights.

Results for the different subgroups will be presented descriptively.

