### **13.1 Timing, Dose, Size and Intensity**

The efficacy endpoints pertaining to timing of administration, dose, and intensity (signal-to-background ratio SBR), along with the surgeon rating scale will be assessed throughout enrollment into Cohorts A1-A6 to determine the final dose for use in Cohorts B1 and B2. These efficacy endpoints will also be used to evaluate the effect of timing of administration of ALM-488 by comparison of Cohort B1 and B2. The following analyses are planned for these efficacy endpoints:

- For each Cohort, SBR will be averaged to get a single mean ratio per patient; then a paired t-test or Wilcoxon signed rank test will be used, as appropriate, to compare SBR between FL and WLR.
- SBR will be also listed by cohort type, and surgery type and device for both FL with WLR.
- Image intensity ratios will also be analyzed with repeated measures analysis of variance (RMANOVA) with timing, image, method (FL /WLR), and device (Zeiss/OnLume) as the repeated factors in the model.
- SBR for FL and WLR measurements will be plotted. Values to the right of the line will indicate that there is improved visualization with FL images and values to the left of the line will indicate that there is improved visualization with WLR images(Equal performance of FL versus WLR will be indicated by dashed line (slope = 1)].
- To further assess timing, Cohorts B1 and B2 will be compared. Image ratios will be averaged to get a single mean ratio per patient; then an unpaired t-test or Wilcoxon rank sum test will be used, as appropriate, separately for FL and WLR.

Paired t-tests will be used unless markedly non-normal data is observed including bimodal or other severe assumption violations; minor skewness is robust to the paired t-test and RMANOVA assumptions. If extreme skewness with outliers, or bimodal distributions are observed, then a Wilcoxon signed rank test will be used instead of a paired t-test and RMANOVA will be performed on the ranked data.

Similarly, unpaired t-tests will be used unless markedly non-normal data is observed including bimodal or other severe assumption violations; minor skewness is robust to the unpaired t-test assumptions. If extreme skewness with outliers, or bimodal distributions are observed, then a Wilcoxon rank sum test will be used instead.

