The optimal cut-off points of SBR and the ability to detect the nerve will be studied using ROC (Receiver Operating Characteristics) curves analyses through logistic regression. In the logistic regression the outcome variable will be the categorized surgeon rating scale 1 : I do not see the nerve versus 4 to 5 : the nerve is visible. The Youden J index given by  $J = \text{Sensitivity} - (1 - \text{Specificity})$  will be used to select the optimal predicted probability cut-off. It is the maximum vertical distance between ROC curve and diagonal line. This will allow to maximize the difference between True Positive and False Positive. All possible SBR values and the corresponding sensitivity and specificity will be obtained using proc logistic in SAS [1]. The optimal cut-off will be determined overall and by device and individual Cohorts (i.e., Cohorts: A, A1, A2, A3, A4, A5, A6, B, B1, B2).

Image intensity ratios will be plotted against nerve diameter, with ratios on the y-axis and diameters on the x-axis. Plots will be displayed overall and by device and individual Cohorts (i.e., Cohorts: A, A1, A2, A3, A4, A5, A6, B, B1, B2).

QMS Document Name: Statistical Analysis Plan	Page 19 of 29
QMS No (include version ref): STF-015-GL.02	Document date: 09JUL2019
CONFIDENTIAL	

Image intensity ratios will be summarized separately for images with and without overlying tissue, overall and by device and individual Cohorts (i.e., Cohorts: A, A1, A2, A3, A4, A5, A6, B, B1, B2).

In the subset of images with overlying non-nerve tissue, depth will be measured via the amount of overlying tissue that there can be to still maintain the ratio of nerve to non-nerves. Depth will be summarized overall and by device and individual Cohorts (i.e., Cohorts: A, A1, A2, A3, A4, A5, A6, B, B1, B2).

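### No SBR test in SAP 13.1 has a term for overlying tissue or nerve diameter, so a systematic difference in image mix between B1 and B2 can pass for a timing effect; the RMANOVA also lists timing and image as repeated factors

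*SAP*

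**What the plan says.** SAP 13.1 plans three inferential analyses of SBR:

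- Within cohorts, FL against WLR: "SBR will be averaged to get a single mean ratio per patient; then a paired t-test or Wilcoxon signed rank test will be used".
- B1 against B2: "Image ratios will be averaged to get a single mean ratio per patient", and "then an unpaired t-test or Wilcoxon rank sum test will be used, as appropriate, separately for FL and WLR".
- An RMANOVA on image intensity ratios "with timing, image, method (FL /WLR), and device (Zeiss/OnLume) as the repeated factors in the model".

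None of the three names overlying tissue, nerve diameter, nerve or surgery type as a term. SAP 8.2 says "No stratified analyses are planned for this study"; the text of that section available for review names no covariate.

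Both variables are handled elsewhere, descriptively. SAP 6.3 makes each an exploratory objective. SAP 8.3 says "For the efficacy analysis, the subgroup of images with overlying tissue will be explored" and presents subgroup results descriptively. SAP 13.1 adds "Image intensity ratios will be summarized separately for images with and without overlying tissue" and "Image intensity ratios will be plotted against nerve diameter", each overall, by device and by cohort.

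Four design facts bear on this. There is no randomisation or blinding (4.2). Each timing cohort has 6 patients and one administration window (4.1, 5). Three surgery types are mixed (10.1). SBR in Cohort A comes from the Zeiss camera only, and in Cohort B from both cameras (13). Each camera can record FL and WLR (8.3), but the SAP text does not say whether both modes, or both cameras, take the same fields.

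**The concern.** The SAP treats two features of an image as possible drivers of SBR and then leaves them out of every SBR test. The B1 v B2 comparison, which serves a secondary objective, reduces each patient to one mean over whatever images were taken. Nothing in the design balances that mix between the two cohorts. If one cohort has more images taken through tissue, or more thin nerves because of the procedures performed, its mean SBR shifts for a reason unrelated to timing.

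The descriptive displays pool images across patients, so a contrast of covered with exposed images mixes differences within and between patients. The two exploratory objectives therefore get no within-patient estimate.

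The RMANOVA sentence is also hard to implement. If timing means the timing cohort, each Cohort B patient has only one level of it. Image numbers have no stated common meaning from one patient to the next. No nesting or error structure is given.

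**Working it through.** **1. The plan's own figure.** From SAP 4.1: 3 cohorts x 3 = 9, 6 x 6 = 36 and 2 x 6 = 12, so 9 + 12 = 21 to 36 + 12 = 48. This reproduces. The SAP text gives no SBR effect size, SD or power. For 6 v 6 at two-sided 5%, 80% power needs (1.96 + 0.84) x sqrt(2/6) = 1.62 SD by normal approximation. By noncentral t with 10 df, 1.8 SD gives 80.2%. Only a large timing effect is detectable.

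**2. Shift on the ratio scale (assumed inputs).** If tissue multiplies SBR by f and the covered share differs by d, the geometric mean ratio with no timing effect is f^d. With d = 0.30, this is 0.5^0.30 = 0.81 or 0.7^0.30 = 0.90. The SAP averages raw ratios. With f = 0.5 the raw ratio is (1 - 0.5 p2)/(1 - 0.5 p1): 0.85/1 = 0.85 for shares 0 v 30%, and 0.50/0.65 = 0.77 for 70% v 100%.

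**3. Timing test, no true effect (simulation, 4000 runs per setting).** Image SBR = patient effect (SD 1) + delta x covered + image error (SD 1), with 6 images per patient and 6 v 6 patients. All these values except the 6 v 6 are assumptions. The test is the SAP's unpaired t on patient means. The adjusted version first removes the within-patient tissue slope, as a simple stand-in for a mixed model. Expected bias is delta x share difference. Simulation error near 5% is sqrt(0.05 x 0.95/4000) = 0.3 points.

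| Covered share, B1 / B2 | Bias at delta -1, -2, -3 | False positives, unadjusted | False positives, adjusted |
|---|---|---|---|
| 50% / 50% | 0, 0, 0 | 4.9%, 4.9%, 5.2% | 4.8%, 5.0%, 5.1% |
| 40% / 60% | -0.2, -0.4, -0.6 | 6.0%, 8.8%, 12.8% | 5.4%, 4.8%, 5.3% |
| 25% / 75% | -0.5, -1.0, -1.5 | 10.9%, 27.6%, 51.1% | 5.5%, 5.5%, 5.8% |

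**4. Chance differences in mix.** With equal expected shares p, the variance of a patient mean is 1 + 1/6 + delta^2 x p(1 - p)/6. At delta = -3 and p = 0.5 this is 1 + 0.167 + 0.375 = 1.542, so the SD of the cohort difference is sqrt(2 x 1.542/6) = 0.72 (simulated 0.71). Without the tissue part it is sqrt(2 x 1.167/6) = 0.62 (simulated 0.62 after adjustment). Chance mix costs precision and leaves the error rate at its nominal level.

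**5. Device, Cohort B.** If the cameras image different fields with covered shares 40% v 60%, false positives are 15% to 46%; at 25% v 75% they are 70% to 99.8%. If both image the same fields, they are 4.6% to 5.6%.

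**6. FL v WLR.** With the same fields in both modes and an equal tissue effect, the mix cancels: bias 0, false positives 4.3% to 5.2%. If tissue lowers FL only, the mean FL - WLR difference is delta x covered share, from -0.25 (delta -1, share 25%) to -1.51 simulated (delta -3, share 50%).

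**7. Image as a repeated factor.** In a balanced layout with image crossed with patient, the RMANOVA timing F equals the squared t on patient means (0.2093 in both). Crossing therefore does not create the bias in step 3.

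**The case against.** The strongest reply is that chance variation in image mix already sits in the between-patient variance of the t-test. That is right, as step 4 shows: inflation needs a systematic B1/B2 difference. Lack of randomisation permits one, but nothing in the documents shows one.

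The SAP also summarises SBR with and without overlying tissue by cohort and by device, so a gross imbalance would probably be visible. That stands, but seeing an imbalance does not correct the tests. A descriptive presentation of exploratory objectives in so small a study is also a defensible choice.

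Four stronger readings may tempt a reader, and the documents do not support them:

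- That the mix confounds FL v WLR. It does not if fields are shared and tissue acts equally on both modes. If tissue acts more on FL, the size of the difference depends on the mix, which is effect modification.
- That device is affected throughout. Cohort A uses one camera, and Cohort B is affected only if fields are unmatched.
- That calling image a repeated factor causes the bias. The SAP does not use the word crossed, and step 7 shows that crossing is not the source.
- That many patients would be lost to empty cells. This depends on the procedure used and on the cell counts, and the SAP states neither.

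Two limits remain. Overlying tissue is classified by image, but the SAP does not say that diameter is recorded per image. SAP text directly after 8.2, and protocol text beyond the eligibility criteria, were not available for this review. They may name covariates or field-matching rules, so their absence from the plan cannot be asserted.

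**Conclusion.** The point holds in a limited form. The SBR analyses specified in SAP 13.1 omit two variables that the SAP itself treats as possible drivers of SBR. In a non-randomised 6 v 6 comparison, a systematic difference in image mix can be read as a timing effect, and a chance difference adds avoidable noise. In Cohort B the same holds for device if the cameras do not share fields. The bias comes from the omitted covariates.

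The sizes (6% to 51% false positives for timing; a ratio of 0.81 or 0.90) rest on assumed tissue effects, shares, SDs and image counts. They show direction and range and do not forecast this trial.

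Separately, the RMANOVA is mis-specified for Cohort B: timing cohort varies between patients, and image belongs within patient. This is an inexpensive improvement worth making. It does not invalidate the plan.

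**What to change.** Replace the RMANOVA by a linear mixed model on image-level log SBR, using all evaluable images:

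- timing cohort as a between-patient factor;
- method and, in Cohort B only, device as within-patient factors;
- overlying tissue and, where recorded per image, nerve diameter as covariates;
- cohort-by-method and tissue-by-method interactions;
- random effects for patient and for nerve or image within patient.

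The cohort-by-method term is needed because the SAP tests timing separately for FL and WLR. Without it, a balanced model averages the two modes: a timing ratio of 0.81 in FL alone would appear as sqrt(0.81) = 0.90.

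Report the adjusted B1 v B2 contrast separately for FL and WLR, the overlying-tissue effect and the diameter slope, each with a 95% CI and labelled exploratory. Keep the planned patient-mean tests alongside. State whether fields are matched across modes and across cameras.

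The cost is SAP wording, one model, a few degrees of freedom and more dependence on model assumptions with 12 patients. The sample size does not change.

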### 7.3 Exploratory Endpoints

To evaluate the ability of imaging techniques (i.e. camera systems) to distinguishing nerve tissue from non-nerve tissue, the following endpoints will be evaluated:

- Ability to detect fluorescence will be studied by determining an optimal cut-off using Youden index and receiver operating characteristic ROC curve analysis.

This endpoint will be summarized separately for each device and each of the Cohorts A1-A6, B1 and B2, as well as overall for Cohort A and Cohort B.

To evaluate the intensity of signal of fluorescence relative to nerve diameter, the following endpoints will be evaluated:

- Intensity (signal-to-background ratio SBR)
- nerve diameter

These endpoints will be plotted against each other, separately for each device and each of the Cohorts A1-A6, B1 and B2, as well as overall for Cohort A and Cohort B.

To evaluate the intensity of signal of fluorescence when there is overlying tissue, the following endpoints will be evaluated:

- Signal-to-background ratio)

This endpoint will be summarized separately for images and each of the Cohorts A1-A6, B1 and B2 as well as overall for Cohort A and Cohort B.

To evaluate surgeon confidence and operative time with a surgeon rating scale, the following endpoints will be evaluated:

- Surgeon confidence will be captured via the surgeon rating scale (1=do not see nerve compared to WLR, 2=see nerve less well compared to WLR, 3=See nerve equally well

QMS Document Name: Statistical Analysis Plan	Page 12 of 29
QMS No (include version ref): STF-015-GL.02	Document date: 09JUL2019
CONFIDENTIAL	

compared to WLR, 4=See nerve better compared to WLR, 5=See nerve much better compared to WLR) for each image.

- For each surgery, the following yes/no question will be asked: “Outside of a clinical trial setting with all the required extra documentation, would this technology have saved you operative nerve-dissecting time compared to WLR?”

Surgeon confidence will be summarized by image, while time saving (yes/no) will be summarized by patient.

Surgeon confidence will be summarized for each device and each of the Cohorts A1-A6, B1 and B2, as well as overall for Cohort A and Cohort B.

Time saving (yes/no) will be for each of the Cohorts A1-A6, B1 and B2, as well as overall for Cohort A and Cohort B.

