### **13.2 Surgical Imaging Worksheet/ Rating Scale**

Surgeon confidence will be captured via the surgeon rating scale (1=do not see nerve , 2=see nerve less well compared to WLR, 3=see nerve equally well compared to WLR, , 4=see nerve better compared to WLR, 5=see nerve much better compared to WLR ) for each image. Surgeon confidence will be summarized overall and by device, individual Cohorts (i.e., Cohorts: A, A1, A2, A3, A4, A5, A6, B, B1, B2) as well surgery type.

Image intensity ratios will also be correlated with the surgeon rating scale using Pearson correlation coefficients unless markedly non-normal data is observed including bimodal or other severe assumption violations; otherwise Spearman correlation coefficients will be used. Correlation coefficients will be presented overall and by device and by individual Cohorts (i.e., Cohorts: A, A1, A2, A3, A4, A5, A6, B, B1, B2).

A listing will be provided.

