#### EFFICACY

- Table 14.2.2.1 SBR comparison between FL and WLR, Zeiss camera Cohort A Analysis Set: FAS
- Table 14.2.2.2 SBR comparison between FL and WLR, Cohort B Analysis Set: FAS

- Table 14.2.3.1 SBR comparison between FL and WLR – Zeiss Image Analysis, Cohort A Analysis Set: FAS
- Table 14.2.3.2 SBR comparison between FL and WLR – Image Analysis, Cohort B Analysis Set: FAS

- Table 14.2.4.1 SBR comparison between B1and B2 – FL Analysis Set: FAS

- Table 14.2.4.2 SBR comparison between B1 and. B2– WLR Analysis Set: FAS

- Table 14.2.5.1 Surgeon Rating Scale, Cohort A Analysis Set: FAS

- Table 14.2.5.1 Surgeon Rating Scale, Cohort B Analysis Set: FAS

- Table 14.2.6.1 Correlation Between Surgeon Rating Scale and SBR for Zeiss device, Cohort A - Analysis Set: FAS

- Table 14.2.6.2 Correlation Between Surgeon Rating Scale and SBR, Cohort B Analysis Set: FAS

- Table 14.2.7.1 SBR and Surgeon Rating Scale for Zeiss device Cohort A, FL Analysis Set: FAS

- Table 14.2.7.2 SBR and Surgeon Rating Scale Cohort B, FL Analysis Set: FAS

- Table 14.2.8 Optimal cut-off point of SBR Cohort A and B, FL- Analysis Set: FAS

- Table 14.2.9.1 Surgeon nerve dissecting time saved, Cohort A Analysis Set: FAS

- Table 14.2.9.1 Surgeon nerve dissecting time saved, Cohort B Analysis Set: FAS

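### The ROC for nerve detection compares rating 1 with ratings 4-5 and leaves out ratings 2-3, in which the nerve is seen; if SBR rises with rating, sensitivity and Youden J are overstated

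*SAP*

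**What the plan says.** SAP Section 13.1 sets the purpose: "The optimal cut-off points of SBR and the ability to detect the nerve will be studied using ROC" curves, fitted through logistic regression. The outcome is the "categorized surgeon rating scale 1 : I do not see the nerve versus 4 to 5 : the nerve is visible". The cut-off is the one that maximises Youden's J, and "All possible SBR values and the corresponding sensitivity and specificity will be obtained using proc logistic in SAS".

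The rating scale appears twice. Section 13.2 defines the two middle categories as "2=see nerve less well compared to WLR, 3=see nerve equally well compared to WLR". Section 7.3 has the same scale with a different wording of the lowest category: "1=do not see nerve compared to WLR, 2=see nerve less well compared to WLR, 3=See nerve equally well". In Section 13.2, rating 1 carries no reference to white light reflectance (WLR).

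Section 7.3 lists one endpoint for the objective of distinguishing nerve from non-nerve tissue: "Ability to detect fluorescence will be studied by determining an optimal cut-off using Youden index and receiver operating characteristic ROC curve analysis". The output is "Table 14.2.8 Optimal cut-off point of SBR Cohort A and B, FL- Analysis Set: FAS".

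No section supplied assigns ratings 2 and 3 to a class in this analysis, gives a reason for leaving them out, or plans a second coding.

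**The concern.** The stated purpose, the scale and the coding do not agree. If the question is whether the surgeon can detect the nerve, the scale splits between rating 1 (not seen) and ratings 2-5 (seen, to varying degrees relative to WLR). The planned outcome sets the clearest positives against the negatives and drops the middle. Removing intermediate cases in this way usually makes a marker look more accurate than it is over all the cases to which it would be applied.

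At stake is the accuracy attached to the SBR cut-off in Table 14.2.8. A reader who takes that cut-off into later work would expect its sensitivity to hold for all images in which the nerve is seen. It need not.

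**Working it through.** **Inputs.** From the SAP: the coding (1 v 4-5), the meaning of each rating, and the criterion J = sensitivity - (1 - specificity). The SAP states no sensitivity, J or cut-off, so there is no planned figure to reproduce. It also gives no rating frequencies, SBR spread or SBR-rating correlation; these are assumed below.

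**Step 1: exact relation.** Let S_k(c) be the proportion of images in rating group k with SBR above cut-off c, and let w be the share of ratings 2-5 that are 2 or 3.

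- Planned: Se = S_45(c)
- All nerve-seen images: Se = w S_23(c) + (1 - w) S_45(c)
- Planned minus all nerve-seen: w [S_45(c) - S_23(c)]

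The negatives (rating 1) are the same in both, so specificity at c is the same and J differs by the same amount. If S_23(c) ≤ S_45(c) at every c, the maximum J under the planned coding is also at least as large.

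**Step 2: worked example (assumed).** Ratings 1 to 5 in proportions 10/15/25/30/20%. The rating is a cut latent normal variable with correlation 0.5 with a normal SBR.

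- w = (15 + 25)/90 = 0.444
- At the planned cut-off: Se(4-5) = 0.754, Se(2-3) = 0.479, specificity = 0.765
- Excess sensitivity: 0.444 × (0.754 - 0.479) = 0.122, so Se(2-5) = 0.632
- Planned J: 0.754 + 0.765 - 1 = 0.519
- J for 1 v 2-5 at the same cut-off: 0.632 + 0.765 - 1 = 0.397
- Maximum J for 1 v 2-5 at its own, slightly lower cut-off: 0.400

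**Step 3: range over assumptions.**

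Model 1 is the latent normal model of Step 2, with correlations 0.3, 0.5 and 0.7 and these mixes (%): 10/5/5/45/35, 20/5/5/40/30, 30/5/5/35/25; 10/10/10/40/30, 20/10/10/35/25; 10/15/25/30/20, 20/20/20/25/15, 30/20/20/20/10.

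Model 2 uses normal groups with SD 1: rating 1 at mean 0, ratings 4-5 at d = 1, 1.5 or 2, ratings 2-3 at f × d, and 10% of images rated 1, so w = (share rated 2-3)/0.9.

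| Planned minus 1 v 2-5 | 10% rated 2-3 | 20% | 40% |
|---|---|---|---|
| Model 1: maximum J | 0.018 to 0.047 | 0.036 to 0.088 | 0.072 to 0.183 |
| Model 1: sensitivity at the planned cut-off | 0.018 to 0.047 | 0.036 to 0.090 | 0.073 to 0.198 |
| Model 1: sensitivity, each coding at its own cut-off | 0.01 to 0.04 | 0.02 to 0.06 | 0.05 to 0.11 |
| Model 2: maximum J, f = 0.25 to 0.75 | 0.010 to 0.059 | 0.021 to 0.118 | 0.041 to 0.233 |
| Model 2: maximum J, f = 1 | 0 | 0 | 0 |
| Model 2: maximum J, f = 1.25 to 1.5 | -0.009 to -0.018 | -0.018 to -0.037 | -0.037 to -0.078 |

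**Step 4: the cut-off.** In Model 1 the planned cut-off lies 0.01 to 0.21 SD above the one for 1 v 2-5. Using it for 1 v 2-5 costs at most 0.0005, 0.0020 and 0.0142 of J at 10%, 20% and 40% rated 2-3. The shift can be larger: with equal numbers in each rating and SBR rising one SD per rating step, the cut-offs are 1.68 and 1.21, and the loss is 0.678 - 0.646 = 0.032.

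**Step 5: the other full coding.** If the intended contrast is better than WLR (1-3 v 4-5), J in the Step 2 example is 0.333. That is also below the planned 0.519.

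**The case against.** The strongest reply is that 1 v 4-5 is a prespecified contrast and its sensitivity and J are correct for that contrast; they are too high only when read as 1 v 2-5. That is so. But Section 13.1 presents the analysis as a study of nerve detection and labels the positive class as the nerve being visible, and on the SAP's scale that description covers ratings 2 and 3 too. A deliberate extreme-group contrast should be named as one.

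A second reply is that the scale is relative to WLR and need not rise with fluorescence SBR: a nerve that is bright under both lights could be rated 3. This stands as a limit on direction. The SAP treats the association as something to estimate: "Image intensity ratios will also be correlated with the surgeon rating scale using Pearson correlation coefficients". The bias could be nil or reversed, as the table shows.

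Third, the sensitivity gap at a fixed cut-off overstates the change in the reported value, because each coding would choose its own cut-off. This also stands: the gap is then smaller, specificity falls a little, and sensitivity can even rise in a given sample. In simulated sets of 60 images it did so in 6% to 20% of sets. The result for J does not depend on this.

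Finally, the endpoint is exploratory, ratings 2-3 do appear in the rating, correlation and SBR-by-rating tables (14.2.5.1, 14.2.6.1-2, 14.2.7.1-2), and Section 2.1 puts table specifications in a separate document, so the full content of Table 14.2.8 is not known. These points limit the harm. They do not change the coding written in Section 13.1.

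**Conclusion.** The concern holds. As written, the ROC does not measure nerve detection over all rated images. That ratings 2-3 have no class, and that the SAP's scale defines them as nerve seen, is plain from the text, and the relation in Step 1 is exact.

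The direction rests on SBR rising with rating, which is plausible but not established in the documents. The size rests on assumed rating mixes and SBR distributions: J overstated by about 0.02 to 0.18 in Model 1 and 0.01 to 0.23 in Model 2 with intermediate ratings 2-3, zero if ratings 2-5 share one SBR distribution or no image is rated 2-3, and understated by up to 0.08 if ratings 2-3 have the higher SBR. The cut-off also moves, usually at little cost in J.

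This should be corrected, but it does not threaten the trial. The endpoint is exploratory and no dose decision rests on this ROC. It is, however, the only endpoint listed for the nerve versus non-nerve objective. A related limit is that background tissue enters only through the SBR predictor and never as a negative class, so the ROC shows how well SBR agrees with surgeon-rated visibility, not how well nerve is told from non-nerve tissue.

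**What to change.** In SAP Section 13.1:

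- Define the detection outcome as rating 1 (nerve not seen) v ratings 2-5 (nerve seen), so that every rated image has a class.
- Keep 1 v 4-5 only as a sensitivity analysis, labelled as an extreme-group contrast.
- If better than WLR is also of interest, add 1-3 v 4-5 as a separate analysis under that name.
- Describe the ROC as agreement of SBR with surgeon-rated visibility.

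In Table 14.2.8, report the number of images rated 2-3 beside the ROC results. In Sections 7.3 and 13.2, use one wording for rating 1.

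The cost is SAP wording and the recoding of one outcome variable from ratings and SBR values already collected. If SBR does rise with rating, J will be less favourable, and sensitivity will generally be so too.
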